### 7.2 Interim Analysis

Not Applicable

### 7.3 Handling of Missing Data

Missing results/events will not be imputed

Adverse events and concomitant medications with completely or partially missing assessment dates will have imputation performed as explained below for the purposes of calculation of durations or relativity to study medication.

For the end of a concomitant medication or adverse event:

- **If only Day of end date is missing:**

The last date of the month and year reported or the date of the final contact with the subject, whichever is earlier, will be used as the end date;

- **If Day and Month of end date are missing:**

The last date of year i.e. December 31 of the year reported or the date of the last study contact with the subject, whichever is earlier, will be used as the end date;

- **If Year of end date or complete end date is missing:**

If the adverse event or concurrent medication continues after the last study contact date, then no end date or time will be estimated.

For the start of a concomitant medication or adverse event:

- **If only Day of start date is missing:**

- If the start year and month of medication/event are the same as that for the first dose date, then following approach will be used:

- If the end date of medication/event is NOT before the first dose date or end date of medication/event is completely missing, then
  - Impute the start day as the day of first dose date;
- Otherwise, impute the start day as 1.

- If the start year and month of medication/event are NOT same as that for the first dose date, then

- Impute the start day as 1.

- **If Day and Month of start date are missing:**

- If start year of medication/event is same as first dose year, then following approach will be used:

i. For medication, impute the start Month as January and the Day as 1;

ii. For adverse event,

- If the end date of event is NOT before the first dose date or end date of event is completely missing, then
  - Impute the start Month and Day as the Month and Day of first dose date;
- Otherwise, impute the start Month as January and the Day as 1;

- If start year of medication/event is NOT same as first dose year, then

- Impute start Month as January and the Day as 1.

- **If Year of start date or complete start date is missing:**

If the year of start of medication/event is missing or start date is completely missing then no start date or time will be imputed.

Also for AE, compare the end date to the first dose date. If the AE end date is before the first dose date then the AE should be considered as a medical history. Otherwise, the AE will be considered as TEAE.

## 8. Statistical Analysis

### 8.1 Patient Disposition

A tabular presentation of the patient disposition will be provided. It will include the number of patients screened, enrolled/ assigned treatment, completed, as well as the number of dropouts, with reasons for discontinuation. All patients entered in the study will be accounted for in this. A listing will be presented to describe dates of screened,

assigned treatment, screen failed with reason, completion, early withdrawal, and the reason for early discontinuation, if applicable, for each patient.

## 8.2 Demographic and Baseline Characteristics

Demographic and baseline characteristics data will be listed and summarized as appropriate using the safety analysis set.

## 8.3 Medical and Surgical History

Medical and Surgical history data will be listed and summarized by System Organ Class and Preferred Term according to MedDRA version 23.0 using the safety analysis set.

## 8.4 Prior and Concomitant Medications

Prior medications/procedures are those that are taken only prior to initial dose of study drug and concomitant medications/procedures are those taken while on study drug including the ones that started before the initial dose of study drug.

All prior and concomitant medications will be coded by Anatomic Therapeutic Class (ATC) and Preferred Term (PT) according to the World Health Organization (WHO) Drug Dictionary version March 1, 2020 and all prior and concomitant procedures will be coded using MedDRA Version 23.0.

Subjects using various prior or concomitant medications or who have undergone prior or concomitant procedures will be listed and summarized with numbers and percentages by ATC level 2 and Preferred Terms.

## 8.5 Study Drug Exposure

The extent of exposure to the study medication will be summarized and listed for safety analysis set. The extent of exposure to the study medication will be calculated as below:

Exposure (days) = Last date of dosing – First date of dosing + 1.

## 8.6 Efficacy Analysis

Not Applicable

## 8.7 Safety Analysis

### 8.7.1 Adverse Events

All adverse events (AEs) will be coded by System Organ Class (SOC) and Preferred Term (PT) according to the Medical Dictionary for Regulatory Activities (MedDRA) Version 23.0. The intensity of adverse events is graded by the National Cancer Institute (NCI) Common Terminology Criteria for Adverse Events (CTCAE) version 4.0 or higher.

*Treatment-emergent adverse events are adverse events with onset during the treatment phase or that are a consequence of a pre-existing condition that has worsened since baseline. All reported adverse events will be*

*included in the analysis. For each adverse event, the percentage of subjects who experience at least 1 occurrence of the given event will be summarized.*

*Any AE occurring before treatment with osimertinib will be included in the data listings but will not be included in the summary tables of AEs. Any AE occurring within 28 days of discontinuation of investigational product (i.e., the last dose of osimertinib) will be included in the AE summaries.*

*Any events in this period that occur after a patient has received further therapy for cancer (following discontinuation of osimertinib) will be flagged in the data listings.*

*Adverse events of special interest (for example interstitial lung disease/pneumonitis-like events; QTc prolongation events) will be summarized separately.*

*Summaries, listings, datasets, or subject narratives may be provided, as appropriate, for those subjects who die, who discontinue treatment due to an adverse event, or who experience a severe or a serious adverse event.*

An overall summary will be provided in terms of count and percentages for:

- AEs
- TEAEs
- Grade 3 and above TEAEs
- Grade 3 and above related TEAEs
- Treatment-related TEAEs
- Treatment-related serious TEAEs
- TEAEs leading to dose change/ interruption/ discontinuation
- Treatment related TEAEs leading to dose change/ interruption/ discontinuation
- Serious TEAEs
- Fatal TEAEs
- Related Fatal TEAEs

Summaries in terms of count and percentages by SOC and PT will be provided for the following:

- TEAEs
- Treatment-Emergent SAEs
- Grade 3 and above TEAEs
- Treatment-related TEAEs
- Grade 3 and above treatment-related TEAEs
- TEAEs leading to dose change/ interruption/ discontinuation
- Adverse Events of special interest

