The primary objective of the trial is to describe the safety profile of osimertinib in routine clinical practice and add to the limited burden of safety data on osimertinib currently available as assessed by the incidence of adverse events (AEs) (Serious and Non-serious AEs) observed during trial. Considering the epidemiology of metastatic NSCLC- adenocarcinoma subtype which are positive for EGFR sensitizing mutation and have progressed after EGFR-TKI based treatment in first line setting and prevalence of T790M-mutation after such progression, a sample size of 60 patients is expected to provide the following exact two sided 95% confidence interval for a list of percentages of patients reporting at least one AE (Julious and Campbell 2012).

Observed rate expressed as % (number of patients reporting at least one AE*)	Lower Limit of CI (%)	Upper Limit of CI (%)
0%	0	6.0
1%	0	7.8
2%	0.1	9.5
5%	1.0	13.9
10%	3.8	20.5
20%	10.8	32.3
30%	18.8	43.2
40%	27.6	53.5
50%	36.8	63.2

^{*}the symptom could be any of the expected AE, unexpected AE or SAE. The calculation is based on the link between binomial and beta distributions.

Hypothesis

No formal hypothesis testing will be conducted.

Statistical Analysis

Data will be summarized using descriptive statistics. Continuous variables will be summarized using the number of observations, mean, SD, coefficient of variation, median, and range as appropriate. Categorical values will be summarized using the number of observations and percentages as appropriate. Shift tables will be provided to determine the change in reported outcomes from baseline.

The safety analysis population will include all patients who sign the ICF and receive at least one dose of osimertinib.

Adverse Events (both in terms of MedDRA preferred terms and CTCAE grade) will be listed individually by patient. Any AE occurring before treatment with osimertinib will be included in the data listings but will not be included in the summary tables of AEs.

Any AE occurring within 28 days of discontinuation of study drug (ie, the last dose of osimertinib) will be included in the AE summaries. Any events in this period that occur after a patient has received further therapy for cancer (following discontinuation of osimertinib) will be flagged in the data listings.

TIME AND EVENTS SCHEDULE

Table 1. Time and Event Schedule

Study Phase	Screening Phase ^(a)	Treatment Phase		Follow-up Phase
Cycle	1 muse	Cycles 1-6	EOT	EOS

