Visit No.	1	2-7 (Day 1 of each cycle)	8	202
Study Days	-6 to 0	1-109 (21 day per cycle)	131	28 days post- EOT
Screening/Enrolment visit				
Informed consent ^(b)	Patients r	nust sign the informed conser procedures are p		study-specific
Eligibility Criteria	X			
Demographics/ Review medical history	X			
WHO Performance Status	X	X	X	
General Physical examination	X	Symptom-directed physical	examination only	
Concomitant medication recording	Continuous from time of ICF until 28 days after last osimertinib dose in treatment phase.			
Study Drug Administration				
Osimertinib dosing		The recommended dose is 80 mg osimertinib once a day until disease progression or unacceptable toxicity. Each cycle is of 21 days.		
Disease Evaluations (Disease char	racteristics wil	ll be performed as per routine	clinical practice)	
Baseline Disease Characteristics	X			
Safety Evaluations				
Physical examination	X	Symptom-directed physical examination only		
Vital parameters	X	X	X	
Adverse event monitoring		us from time of ICF until 28 days after last study osimertinib dose		
12-lead ECG	X	X	X	
Hematology & Biochemistry	X	X	X	

Footnotes:

- a. The Screening Phase begins when the first Screening procedure is conducted. Screening tests should be performed within 7 days of Cycle 1 Day 1 except for disease evaluations (performed as routine clinical practice).
- b. Must be signed before first study-related activity.

TABLE OF CONTENTS

PAGE

TITLE	PAGE	1
VERSIO	ON HISTORY	2
PROTO	COL SYNOPSIS	3
TIME A	AND EVENTS SCHEDULE	8
TABLE	OF CONTENTS	9
1.	Introduction	13
1.1	Background and rationale for conducting this study	13
1.2	Rationale for study design, doses and control groups	14
1.3	Benefit/risk and ethical assessment	14
1.4	Study Design	14
2.	Study Objectives	14
3.	Patient Selection, Enrolment, Randomisation, Restrictions, Discontinuation and Withdrawal	15
3.1	Inclusion criteria	15
3.2	Exclusion criteria	15
3.3	Patient enrolment and randomization	15
3.4	Procedures for handling incorrectly enrolled or patients	16
3.5	Methods for assigning treatment groups	16
3.6	Methods for ensuring blinding	16
3.7	Methods for unblinding	16
3.8	Restrictions	16
3.9 3.9.1	Discontinuation from study treatment Procedures for discontinuation of a patient from study drug	
3.10 3.10.1	Criteria for withdrawal	
3.11	Discontinuation of the study	18
4.	Study Plan and Timing of Procedures	19
5.	Study Assessments	20
5.1 5.1.1 5.1.2 5.1.3	Safety assessments Laboratory safety assessments Physical examination	21

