6.3.3 Variables

The following variables will be collect for each AE;

- AE (verbatim)
- The date when the AE started and stopped
- Maximum intensity
- Whether the AE is serious or not
- Investigator causality rating against the study drug (yes or no)
- Action taken with regard to study drug
- AE caused patient's withdrawal from study (yes or no)
- Outcome.

In addition, the following variables will be collected for SAEs:

- Date AE met criteria for serious AE
- Date Investigator became aware of serious AE
- AE is serious due to
- Date of hospitalization
- Date of discharge
- Probable cause of death
- Date of death
- Autopsy performed
- Causality assessment in relation to Study procedure(s)
- Causality assessment in relation to Other medication
- Description of AE.

It is important to distinguish between serious and severe AEs. Severity is a measure of intensity whereas seriousness is defined by the criteria in Section 6.2. An AE of severe intensity need not necessarily be considered serious. For example, nausea that persists for several hours may be considered severe nausea, but not a SAE unless it meets the criteria

shown in Section 6.2. On the other hand, a stroke that results in only a limited degree of disability may be considered a mild stroke but would be a SAE when it satisfies the criteria shown in Section 6.2.

Maximum intensity refers to the complete course of the AE. The patient (parents/legal guardians) will be asked to assess the maximum intensity of the reported AEs according to the following scale:

- Mild (awareness of sign or symptom, but easily tolerated)
- Moderate (discomfort sufficient to cause interference with normal activities)
- Severe (incapacitating, with inability to perform normal activities).

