8.3 Description of outcome variables in relation to objectives

Analysis will be conducted to evaluate the following as available in the CRF:

- Baseline characteristics: demographics, relevant medical history, disease characteristics, cancer treatment history.
- Exposure to the study drug
- Adverse events SAEs, AEs leading to dose modification or discontinuation, and AEs of special interest (for example interstitial lung disease/pneumonitis-like events; QTc prolongation events)
- Death due to AE, or unknown cause (except death due to disease progression).

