8.5.1 Analysis of the primary variable (s)

Adverse Events

The verbatim terms used in the CRF by investigators to identify adverse events will be coded using the Medical Dictionary for Regulatory Activities (MedDRA) and CTCAE grade and will be listed individually by patient. Treatment-emergent adverse events are adverse events with onset during the treatment phase or that are a consequence of a pre-existing condition that has worsened since baseline. All reported adverse events will be included in the analysis. For each adverse event, the percentage of subjects who experience at least 1 occurrence of the given event will be summarized.

Any AE occurring before treatment with osimertinib will be included in the data listings but will not be included in the summary tables of AEs. Any AE occurring within 28 days of discontinuation of investigational product (ie, the last dose of osimertinib) will be included in the AE summaries.

Any events in this period that occur after a patient has received further therapy for cancer (following discontinuation of osimertinib) will be flagged in the data listings.

Adverse events of special interest (for example interstitial lung disease/pneumonitis-like events; QTc prolongation events]) will be summarized separately.

Summaries, listings, datasets, or subject narratives may be provided, as appropriate, for those subjects who die, who discontinue treatment due to an adverse event, or who experience a severe or a serious adverse event.

Clinical Laboratory Tests

Laboratory data will be summarized by type of laboratory test. Descriptive statistics will be calculated for each laboratory analyte at baseline and for observed values and changes from baseline at each scheduled time point. Changes from baseline results will be presented in pre- versus posttreatment cross-tabulations (with classes for below, within, and above normal ranges). Parameters with predefined National Cancer Institute Common Terminology Criteria for Adverse Events (NCI-CTCAE) toxicity grades will be summarized. Change from baseline to the worst adverse event grade experienced by the subject during the study will be provided as shift tables. A listing of subjects with any laboratory results outside the reference ranges will be provided. A listing of subjects with any markedly abnormal laboratory results will also be provided.

Electrocardiogram (ECG)

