### 5.2 Visit Schedule

Patient participation will include a Screening/Enrolment Phase, a Treatment Phase, and a Follow-up Phase.

Phase/Visit	Definition
The Screening Phase	Up to 7 days prior to Cycle 1, Day 1.
The Treatment Phase	From Cycle 1, Day 1 to Cycle 6, Day 21; or until study drug discontinuation due to either disease progression or unacceptable toxicity; or other reasons whichever occurs first. Each cycle of treatment is defined as 21 days of once daily Osimertinib treatment.
An End-of-Treatment (EoT) Visit	On Cycle 6, Day 21 of the study drug administration. If disease progression is diagnosed before Cycle 6, Day 21, then the patient will discontinue study drug with completion of the End-of- Treatment Visits on the day of progression, and will enter the Follow-up Phase.

The Follow-up Phase.	It will begin once a patient discontinues study drug or on completion of Treatment Phase, and will continue until 28 days after last dose, death, loss to follow up, consent withdrawal for study participation, or study end, whichever occurs first. This will be considered as End-of-study visit.
----------------------	---

*The observation period including the Enrolment Visit and telephonic end-of-study visit will be up to a maximum duration of approximately 23 weeks for each patient.*

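### SAP 8.7.1 promises that AEs up to 28 days after last dose are summarised, but its treatment-emergent definition omits new-onset AEs in that window from 8 of 11 overall rows and 5 of 7 SOC/PT tables, and SAP 7.3 holds a competing rule

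*SAP*

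**What the plan says.** - **Definition of a treatment-emergent AE (TEAE).** SAP 8.7.1 states: "Treatment-emergent adverse events are adverse events with onset during the treatment phase", with a second part for pre-existing conditions that worsen. The definition is taken from Protocol 8.5.1, which counts "adverse events with onset during the treatment phase or that are a consequence of a pre-existing condition that has worsened since baseline".
- **End of the treatment phase.** SAP 5.2 gives it as "From Cycle 1, Day 1 to Cycle 6, Day 21; or until study drug discontinuation". The 28 days after last dose belong to a separate Follow-up Phase.
- **28-day rule.** SAP 8.7.1 also states: "Any AE occurring within 28 days of discontinuation of investigational product (i.e., the last dose of osimertinib) will be included in the AE summaries". Protocol 8.5.1 has the same rule, and so does the synopsis: "Any AE occurring within 28 days of discontinuation of study drug (ie, the last dose of osimertinib) will be included in the AE summaries".
- **Collection.** Protocol Table 1 has AE monitoring run "from time of ICF until 28 days after last study osimertinib dose", so events in the window will be in the database.
- **Planned outputs.** SAP 8.7.1 lists 11 rows for the overall summary and 7 tables by system organ class and preferred term (SOC/PT). Only the overall row for AEs and the SOC/PT table for AEs of special interest (AESI) are not limited to treatment-emergent events.
- **A second rule.** The closing text of SAP 7.3, which deals with missing data, compares an AE's end date with the first dose date. If the AE ended before first dose it is medical history; if not, it is a TEAE. No upper time limit is given.

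**The concern.** An AE that first appears in the 28 days after the last study dose starts outside the treatment phase, and it is not the worsening of a pre-existing condition. It therefore fails both parts of the SAP 8.7.1 definition, although the same section says it will be summarised.

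This is a safety-only study. Its primary outcome (Protocol section 2) is patients with AEs, SAEs, AESIs and on-study deaths, and Protocol 8.3 lists deaths from an AE or an unknown cause among the outcomes to analyse. Every serious and fatal AE summary on the SAP's two lists is limited to TEAEs. A programmer who follows the definition and one who follows the 28-day rule could report different numbers of patients with serious or fatal events from the same data.

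**Working it through.** **1. The plan's own figure.** Exact (Clopper-Pearson) 95% limits with n = 60 reproduce all nine rows of the table in SAP section 4; for example, 6/60 = 10% gives 3.8 to 20.5. That table is sound and serves only as a yardstick here.

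**2. Which outputs are affected.**

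| | Listed | Limited to TEAEs | Of these, about dose action | Affected |
|---|---|---|---|---|
| Overall rows | 11 | 10 | 2 | 10 − 2 = 8 |
| SOC/PT tables | 7 | 6 | 1 | 6 − 1 = 5 |

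The 8 rows are: TEAEs; Grade 3 and above; Grade 3 and above related; related; related serious; serious; fatal; related fatal. The 5 tables are: TEAEs; SAEs; Grade 3 and above; related; Grade 3 and above related.

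The dose-action outputs are set aside on an assumption. The CRF collects "Action taken with regard to study drug", and an AE that starts after the last study dose should not be able to trigger such an action. If sites recorded actions on commercial osimertinib in that field, the counts would be up to 10 of 11 and 6 of 7.

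**3. What still shows a new-onset follow-up AE.** The overall AE row, the AESI table (so late interstitial lung disease remains visible) and the listings. Narratives or extra summaries for deaths and SAEs are also unrestricted, but SAP 8.7.1 makes them optional. The laboratory worst-grade shift tables are not limited to TEAEs either. Worsening of a pre-existing condition has no end date in the definition, and an AE that starts on treatment and later proves fatal remains a fatal TEAE.

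**4. What SAP 7.3 does to the same event.** Read as a general rule, it makes every follow-up AE a TEAE and contradicts 8.7.1. Read as part of the missing-date rules, where it sits, it makes only follow-up AEs with missing or partial dates TEAEs. A follow-up AE with complete dates is then excluded and one with an incomplete date is included. Neither reading agrees with the 8.7.1 definition throughout.

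**5. Size of the window.** Treatment is 6 × 21 = 126 days, so the window is 28/(126 + 28) = 18.2% of time after first dose for a completer. With illustrative treatment lengths of 84 and 42 days it is 28/112 = 25% and 28/70 = 40%.

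**6. Effect of one patient.** A patient whose only qualifying event falls in the window moves a row by 1/60 = 1.7 points: from 0/60 (95% CI 0 to 6.0) to 1/60 (0.0 to 8.9). A patient who already has a qualifying event on treatment moves it by nothing.

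**7. Illustrative shift.** The documents give no AE rate for follow-up, so both scenarios assume the same constant AE hazard on and off drug.

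- (a) All 60 complete. Shown rate = 1 − (1 − p)^(126/154).
- (b) Drug is stopped only for progression, at an exponential rate with the 10.1-month median PFS quoted in the protocol background. The rate is λ = ln 2/(10.1 × 30.4375) = 0.00225 per day. Then 1 − exp(−126λ) = 24.7% (about 15 of 60) stop before day 126; mean treatment is 0.247/λ = 109.7 days; and the window is 28/(109.7 + 28) = 20.3% of observed time. For each p, the hazard is set so that the rate through the window equals p, and the shown rate is then computed without the window.

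| Rate through day 28 after last dose | Shown, (a) | Shown, (b) | Fewer patients of 60, (b) |
|---|---|---|---|
| 5% | 4.1% | 4.0% | 0.6 |
| 10% | 8.3% | 8.0% | 1.2 |
| 20% | 16.7% | 16.3% | 2.2 |

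**The case against.** The strongest reply is that the plan already covers these events. SAP 8.7.1 says that all reported AEs are analysed, the unrestricted AE row satisfies the 28-day rule literally, and SAP 7.3 would make follow-up AEs treatment-emergent anyway. Part of this stands. A reader might infer that follow-up AEs are definitely excluded, or lost to the study, and the documents support neither. SAP 7.3 can be read to include them, they are collected and listed, and several outputs are unrestricted. Nor can one say that all serious, fatal or Grade 3 and above output is restricted, given the optional narratives and the laboratory shift tables.

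What the reply does not do is settle the rule. One overall row does not fill the serious and fatal rows, and no SOC/PT table of all AEs is listed. SAP 7.3 does not say that it overrides 8.7.1, and its placement suggests that it was meant for incomplete dates.

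It is also fair to object that the size is speculative. An equal hazard off drug has no support in the documents, Protocol 6.3.7 keeps events unequivocally due to progression out of AE reporting, and progression is not the only reason for stopping. That stands, and it is why the figures in step 7 are illustrations only.

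**Conclusion.** The SAP is inconsistent on which follow-up AEs are treatment-emergent. Under the 8.7.1 definition, new-onset AEs in the 28-day window are omitted from 8 of 11 overall rows and 5 of 7 SOC/PT tables, including every listed serious and fatal AE summary, against the section's own 28-day rule. Those counts rest on the dose-action assumption in step 2. SAP 7.3 gives a different answer for some or all of the same events.

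A reader might infer a material bias in the safety results. The documents do not support that: the number of affected events cannot be computed, the illustrative shifts (0.6 to 2.2 patients of 60) are small against intervals such as 3.8 to 20.5 at 10%, and no hypothesis is tested. The practical risk lies in rare serious or fatal events, where one patient decides whether a row reads 0/60 or 1/60. This is a definition that should be corrected before the tables are programmed; it is not a loss of data.

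**What to change.** In the SAP:

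1. In 8.7.1, define a TEAE as an AE with onset, or worsening of a pre-existing condition, from first dose through 28 days after the last study dose, and use this for every TEAE row and table. The word *study* matters. A completer who moves to commercial osimertinib (Protocol 7.2) may not reach a last dose of osimertinib during the study, and Table 1 already counts from the last study dose.
2. Keep the planned flag for onset after further anti-cancer therapy. Optionally, also flag onset while on post-study commercial osimertinib.
3. In 7.3, state that the closing rule applies only to AEs with missing or partial dates and defers to the 8.7.1 definition.

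Protocol 8.5.1 need be aligned only if the protocol is amended for another reason, since Protocol 10.5 requires ethics approval of an amendment. The SAP change follows the protocol's own 28-day rule.

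The cost is a sentence in 8.7.1, a clause in 7.3 and, if wanted, one listing flag. No extra patients, visits or data are needed. The downside is that TEAE counts may rise slightly.
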